Secondary Endpoints	 Procedure success rate defined as the proportion of participants who successfully received the target treatment of at least 6 cm of duodenum treatment Procedure time defined as the time between the Endogenex catheter insertion and catheter removal. Change from baseline in glycemic parameters post procedure by visits HbA1c Fasting plasma glucose (FPG) Insulin resistance by HOMA-IR Post prandial plasma glucose (PPG), Beta cell function, disposition index by mixed meal tolerance test (MMTT) Time in range, glucose variability by continuous glucose monitoring (CGM) Proportion of treated participants with an HbA1c improvement ≥0.5 points from baseline at 24 weeks Proportion of treated participants with an HbA1c improvement ≥0.5 points from baseline at 24 weeks and maintained at 48 weeks Change in weight from baseline by visit Change in glucose-lowering medication usage Change in liver enzymes from baseline at 24 weeks Alanine Aminotransferase (ALT) Aspartate Aminotransferase (AST) Change from baseline in blood pressure and lipid profile by visit 		
Safety Evaluation	Safety will be characterized through a summary of the incidence of adverse events, device- or procedure-related adverse events, and serious device- or procedure-related		
	adverse events.		
Inclusion Criteria	1. 22-65 years of age		
	2. Current diagnosis of T2D3. History of T2D for at least 3 years and less than or equal to 10 years		
	3. History of T2D for at least 3 years and less than or equal to 10 years		

- 4. HbA1C of 7.5-10.0%, inclusive
- 5. BMI 24-40 kg/ m^2 , inclusive
- 6. On two to three non-insulin glucose lowering mediations, with one at maximum tolerated dose and another at half-maximum dose at least, with no changes in medication for at least 12 weeks prior to baseline visit prior to baseline visit
- 7. History of failed attempt to reach glycemic goal by lifestyle modifications
- 8. Weight stability (defined as a < 5% change in body weight) for at least 12 weeks prior to the screening visit
- 9. Agree not to donate blood during participation in the study.
- 10. Able to comply with study requirements and understand and sign the Informed Consent Form
- 11. Women of childbearing potential must be using an acceptable method of contraception throughout the study
- 12. Willing and able to use CGM for the duration of the study and comply with study visits and study tasks as required per protocol.

13.

Exclusion Criteria

- 1. Diagnosed with type 1 diabetes

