6.2.1 Background Glucose-Lowering Medications

Eligible participants must be on two to three non-insulin glucose-lowering medication(s), one at maximum tolerated dose and another at half-maximum dose at least, without a severe hypoglycemic event within the past six months of the screening visit.

Participant's background medication will be kept stable (no change in medication or dose) for at least 12 weeks prior to the Baseline Visit.

Peri-procedurally, the dose of medications with hypoglycemic risks will be adjusted per guidelines provided in **Section 6.2.2**.

Following the transitional diet period, participant's medication will be titrated to the background level and maintained stable until the Week 24 Visit has been completed. Medication and/or dose change necessary for managing hypoglycemia, hyperglycemia, or other safety concerns is permitted. Reason for the medication change must be documented on eCRF.

Following the Week 24 Visit, participants will be managed according to the current (2021) guidelines of the American Diabetes Association² and their glucose-lowering medications will be optimized as necessary to reach an HbA1c target of 7%.

Background medications are non-investigational products. They should be used in accordance with standard of care and their approved labeling. They will not be provided by the sponsor.

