6.2.3 Guidelines for Managing Hyperglycemia

After the background medications have been titrated back to baseline level following the transitional diet period, participants with severe, persistent hyperglycemia should be offered treatment intensification.

In the event of suspected persistent hyperglycemia in a subject based on either symptoms of hyperglycemia (eg, thirst, polyuria, blurred vision), CGM readings of >250 mg/dL for > 30% of the time, or repeated fasting CGM readings above 270 mg/dL (e.g. occurring 3 days in a week), the investigator should perform additional laboratory tests to assess whether rescue therapy is warranted.

Participants meeting the following criteria should be offered rescue medication (i.e. intensification of glucose-lowering background medication and/or initiation of basal insulin).

- FPG > 270 mg/dL, confirmed by repeated measures more than 3 days apart, and no intercurrent cause can be identified, or
- HbA1c is >8.0% AND the interval improvement is <0.5% from baseline, by Week 12

After Week 24, participants should be offered treatment intensification if they do not reach their HbA1c target, which for most individuals is 7.0%.

The above criteria and medications are provided as a guideline. Investigators should always exercise his/her clinical judgement based on individual conditions to protect participant's safety and wellbeing.

Participants who meet rescue criteria before Week 24 should first complete the Week 24 visit activities within 5 days before initiation of the rescue medication to ensure that important trial endpoint measurements are collected and be provided the rescue therapy.

Medication changes and reasons for the changes will be documented on the eCRFs. Medications used to manage hyperglycemia are non-investigational and will not be provided by the sponsor.

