12.4 Statistical Analysis

12.4.1 General Statistical Considerations

Analyses will be performed according to the general principles and directions outlined in these methods.

- Continuous data will be summarized using descriptive statistics: mean, standard deviation, median and range or interquartile range. Categorical variables will be summarized using frequency counts and percentages.
- For events which can occur multiple times in a single subject (e.g., adverse events), summaries
 will be comprised of the number and percentage of subjects with an event and the total number of
 such events. The proportion of subjects with events will be considered primary for analysis
 purposes.
- In general, available data will be used for all analyses, and missing data will not be replaced or
 otherwise imputed in summaries and analyses of study outcomes. However, to avoid biasing
 results due to confounding therapies, effectiveness data collected after an identified initiation of
 rescue medication for hyperglycemia will be replaced by the last value collected prior to such
 rescue intervention.
- Although the study is not explicitly powered to test *a priori* statistical objectives, comparisons citing p-values may be made between baseline metrics to values collected post-intervention, and between subgroups including the two treatment arms. In such cases, p-values will be presented using two-sided tests at a 0.05 level of significance or equivalently one-sided tests at a 0.025 level of significance.

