### 3. INTRODUCTION

This statistical analysis plan (SAP) describes the planned statistical methods to be used during the reporting and analysis of data collected under the Clinical Investigation Protocol entitled Safety and Feasibility of Endoscopic Application of a Novel Therapy for Duodenal Mucosal Regeneration in the Treatment of Type II Diabetes (REGENT-1-US Study), Doc. No. 346. This SAP should be read in conjunction with the study protocol and case report forms (CRFs).

The REGENT-1-US study is a multicenter, open-label, treatment-only study conducted in the United States. The study is designed to assess the feasibility and preliminary safety of the Endogenex device for endoscopic duodenal cellular regeneration in patients with type 2 diabetes (T2D) inadequately controlled on glucose-lowering medications. The protocol enrolled patients who were treated with non-insulin glucose-lowering agents; a tabulation of the treatment and number of patients is presented below.

Device Generation 1 / 600	Device Generation 1 / 600	Device Generation 2 / 750	All
Volts / Single Treatment	Volts / Double Treatment	Volts / Double Treatment	Patients
(n)	(n)	(n)	(n)
3	7	10	20

This plan is developed for analysis and reporting of the 48-week follow up data. The SAP may be revised in the future to address additional follow up data analysis beyond 48 weeks, if necessary.

Patients are considered enrolled in the study once the patient has passed endoscopic screening and proceeded to the Index procedure. *Screen failures* are defined as patients who consented to participate in the clinical study and started the screening tests specified by the protocol but are not subsequently enrolled into the study. Procedure success was defined as at least 6cm of duodenum was successfully treated.

The following analysis populations are defined for the presentation of the results from this study: *Intent-to-Treat* (ITT), *Full Analysis Set* (FAS) [referred to in the study protocol as the modified Intent-to-Treat (mITT) population], *Per-Protocol* (PP) and *Completed Cases* (CC). (Ref. Section 11.3 of the study protocol).

The primary and secondary safety analyses will be performed using the ITT population. The primary effectiveness analyses will be performed using the FAS population. The Per-Protocol population and Completed-Cases population will be used for the sensitivity analyses of the primary and secondary effectiveness endpoints.

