# 7.3. Handling of Missing Data

# 7.3.1. Missing and Censored Data

All tabulations and analyses will be based on the observed data without imputation, with the exception of dates.

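### SAP 7.3.1 drops, without a reason, the protocol's rule for effectiveness values measured after rescue medication, leaving mean changes at Weeks 36 and 48 most exposed

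*SAP*

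**What the plan says.** SAP 7.3.1 sets the rule: "All tabulations and analyses will be based on the observed data without imputation, with the exception of dates". SAP 7 agrees. It confines imputed data to dates and makes observed data the primary presentation. For effectiveness, "The primary effectiveness analyses will be performed using the FAS population" (SAP 3). That set does not exclude patients whose medication changes.

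Protocol 12.4.1 also starts from available data without imputation, but then makes an exception, with the stated aim of avoiding bias from confounding treatment. Effectiveness data gathered after an identified start of "rescue medication for hyperglycemia will be replaced by the last value collected prior to such" intervention.

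Protocol 6.2.3 gives two routes to rescue before Week 24. One rests on confirmed high fasting glucose. The other is "HbA1c is >8.0% AND the interval improvement is <0.5% from baseline, by Week 12". Patients who qualify "should first complete the Week 24 visit activities within 5 days before initiation of the rescue medication". On records, "Medication changes and reasons for the changes will be documented on the eCRFs".

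After Week 24, protocol 6.2.1 says that "their glucose-lowering medications will be optimized as necessary to reach an HbA1c target of 7" per cent, and 6.2.3 offers intensification to those who miss their target. One secondary endpoint in the Protocol Summary is an HbA1c improvement of at least 0.5 points "from baseline at 24 weeks and maintained at 48 weeks".

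**The concern.** An instruction to replace certain observed values and an instruction to impute nothing but dates cannot both be programmed. If the SAP governs, values measured on rescue treatment enter the by-visit estimates as though they reflected the device alone.

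The likely direction is foreseeable. The HbA1c route selects patients who have improved little, and rescue is meant to lower their glucose. Keeping their later values would therefore tend to favour the device. With no control arm, nothing in the design offsets this. The effectiveness results of this feasibility study are descriptive, so what is at stake is whether those descriptions can be read as device effects.

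**Working it through.** **Whether the texts can be reconciled**

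| Question | Protocol 12.4.1 | SAP 7 and 7.3.1 |
|---|---|---|
| Default | Available data, no imputation | Observed data, no imputation |
| Exception | Post-rescue effectiveness values replaced by last pre-rescue value | Dates only |
| Reason given | Avoid bias from other treatment | None concerning rescue |

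The defaults agree; the exceptions do not.

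**Which HbA1c visits are exposed**

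SAP 9 (Third Secondary Endpoint) lists Weeks 4, 12, 24, 36 and 48. Take a rescue soon after Week 12:

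- Weeks 4 and 12 precede rescue.
- Week 24 activities are brought forward to before rescue (protocol 6.2.3).
- Weeks 36 and 48 follow rescue, so 2 of 5 visits are exposed.

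A fasting-glucose rescue before Week 12 would expose Week 12 as well.

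The protection at Week 24 depends on how the record is labelled. SAP 8.6 gives expanded windows of days 73 to 95 for Week 12 and 152 to 184 for Week 24. By those windows, an early assessment on day 90 would be a Week 12 record. Whether they apply is unclear: 8.6 presents them for unscheduled visits, and SAP 7 ties expanded windows to the Level 3 displays. The SAP does not say that the brought-forward record is the Week 24 value.

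**Shift in the mean**

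The documents give neither a rescue rate nor a rescue effect. Let d be the gap between the carried-forward value and the observed post-rescue value, and n the number observed at the visit. Each rescued patient shifts the mean by d/n. Assume d is 0.5 to 1.5 points. Group sizes are the treated counts in SAP 3 (3, 7 and 10; 7 + 10 = 17 in Comparison Set 2; 20 in all).

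| n | 0.5/n | 1.5/n |
|---|---|---|
| 20 | 0.025 | 0.075 |
| 17 | 0.029 | 0.088 |
| 10 | 0.05 | 0.15 |
| 7 | 0.071 | 0.214 |
| 3 | 0.167 | 0.50 |

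The SAP uses a repeated-measures mixed model. A check fit with 10 patients, five visits, an assumed correlation of 0.5 and one Week 36 value lowered by 1.0 gave a shift of 0.100 with complete data (1.0/10). With three of ten missing at that visit it gave 0.143 (1.0/7). Treated counts therefore understate the shift when visits are missed.

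**Responder rates**

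- Eighth endpoint (Week 24 response): a patient rescued by the HbA1c route has improved by less than 0.5. If the pre-rescue assessment is used as Week 24 and agrees with that, the patient is a non-responder under either rule, and the shift is zero. Only if a post-rescue value were used could the patient switch. A prior improvement of 0.4, 0.2 or 0 would then need a further fall of 0.1, 0.3 or 0.5. One switch moves the rate by 100/n: 5.0 points at n = 20, 10.0 at n = 10.
- Ninth endpoint (maintained at Week 48): the SAP leaves Week 24 non-responders out of the tabulation, so the denominator is r, the number of Week 24 responders. The exposed patient is a Week 24 responder who is rescued before Week 48, and each one is worth 100/r. Because r cannot exceed 20, that is at least 5.0 points overall; r itself is unknown.

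**The case against.** The strongest case on the other side has five parts.

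- **The SAP is meant to be read with the protocol, and the study is small.** Reading them together does not say which of two incompatible instructions wins. SAP 3 would also have the protocol's rule labelled unplanned if it were applied without being in the SAP. The small-sample reason in SAP 7 is given for not attempting multiple imputation of missing data. Post-rescue values are not missing.
- **Week 24 is the principal time point for HbA1c, fasting glucose and HOMA-IR, and it is measured before rescue.** This largely stands. A reader might infer that three of five HbA1c visits are contaminated after a rescue just past Week 12, or that every rescued patient moves a responder rate. The documents do not support either: both need a post-rescue Week 24 record, and the protocol schedules none. The meal-test and CGM endpoints have Week 12 as principal time point, which also precedes rescue in that example.
- **The Per-Protocol and Completed Cases analyses already deal with rescue.** In part. A patient rescued before Week 24 fails the stable-medication condition and leaves those sets at every visit, including Weeks 36 and 48. But they are sensitivity sets, and they exclude patients instead of applying the protocol's replacement.
- **Planned optimisation after Week 24 is the larger confounder at Weeks 36 and 48.** It may be. Entry HbA1c is 7.5 to 10.0% and the usual target is 7.0%, so many patients could have treatment intensified. Neither document says whether this counts as rescue for the analysis rule. Until that is settled, the effect of dropping the rule cannot be separated from planned care.
- **Carry-forward is a weak method.** True: it is a single imputation that understates uncertainty. That is a reason to show both analyses, not to drop a pre-specified rule without comment.

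**Conclusion.** The contradiction is certain; its numerical effect is not. The SAP omits a bias-control rule that the protocol prescribes, and as written it would keep any rescued patient's later values in the primary effectiveness estimates. It does not follow that such values will be there: if nobody is rescued, the effect is zero.

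Under an assumed gap of 0.5 to 1.5 HbA1c points, each rescued patient moves an affected visit mean by 0.05 to 0.15 with 10 observed, or 0.025 to 0.075 with 20. The main exposure is by-visit change at Weeks 36 and 48. Responder rates are at risk only if a post-rescue value is taken as Week 24, or if a Week 24 responder is rescued before Week 48.

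The damage is confined to secondary endpoints, for which SAP 9 plans no formal hypothesis tests. The safety primary endpoint is unaffected. This should be corrected before database lock.

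**What to change.** 1. Write the replacement rule of protocol 12.4.1 into SAP 7.3.1 for the primary FAS effectiveness analyses. Derive a rescue flag and start date from the eCRF. Show the observed-data analysis as supplementary, and report the number rescued in each group.
2. State that the assessment completed before rescue under protocol 6.2.3 is analysed as the Week 24 value.
3. State whether medication optimisation after Week 24 counts as rescue for this analysis rule. For the Ninth endpoint, do not let a carried-forward Week 24 value count as maintained at Week 48. Score a Week 24 responder who is given rescue before Week 48 as not maintained, and report how many Week 24 responders had medication intensified.

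The cost is SAP wording and two derived variables, because medication changes and their reasons are already collected. The price is that carry-forward understates uncertainty and some results may look less favourable. Without the limit in step 3, it could also inflate apparent durability at Week 48. The clinical rescue guideline is left as it is, and nothing here settles the Ninth endpoint's threshold.

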# 7.3.2. Subgroup Analyses: Assessing the Effect of Pre-Specified Factors on a Continuous Parameter

Based on the limited enrollment and sample size from the clinical investigation, the proposed tabulations for the individual subgroups may not be possible. Subgroup analyses will follow the follow approach where possible and if it is clinically indicated to address a specific research question.

The breakdown of safety and effectiveness will follow the FDA Guidance entitled *Evaluation and Reporting of Age-, Race-, and Ethnicity-Specific Data in Medical Device Clinical Studies* (Document issued on September 12, 2017). Specifically, the guidance provided in Section VI. entitled *Recommendations for Submitting Age-, Race-, and Ethnicity-Specific Data in Submissions to the Agency and Reporting in Public Documents*, Part A: Enrollment Demographics, Baseline Characteristics & Co-Morbidities.

Subgroup analyses by the following baseline characteristics will be provided if there are a sufficient number of patients that warrant this breakdown:

- age group ( $<65, \ge 65$  years)
- race
- sex
- ethnicity
- duration of diabetes (<median, ≥median)
- duration of diabetes ( $\leq 5$ ,  $\geq 5$  to  $\leq 10$ ,  $\geq 10$  years)
- HbA1c ( $\leq 8.5\%$ , > 8.5%)
- renal impairment (eGFR <60,  $\ge$ 60 mL/min/1.73m2), and
- BMI group ( $<30, \ge 30 \text{ to } <35, \ge 35 \text{ kg/m2}$ ).

# 7.3.3. Safety Measures

Descriptive summaries for all safety measures will be based on observed data. No imputation of missing scores or observations will be implemented for safety outcomes.

# 7.3.4. Dates for Medical Events

The completely or partially missing onset and resolution dates of medical events including AEs will be imputed in a conservative fashion as follows:

Date	Type of Missing Date	Handling of Missing Date
Event onset date	Completely missing	No imputation will be applied.
(e.g., YYYY- MM-DD)	Only YYYY is available	Use the first day of YYYY to impute the missing month and date parts of the onset date
	YYYY and MM are available but DD is missing	Use the first day of MM to impute the missing date part of the onset date
Event resolution date (e.g., YYYY- MM-DD)	Completely missing	No imputation will be applied. The event will be considered ongoing (i.e., not resolved) at the Study Exit date.

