12.4.3 Primary Endpoint Analysis

The primary endpoint of the study is the proportion of participants experiencing one or more device- or procedure-related serious adverse events within 12 weeks post-procedure. The analysis will be performed using the ITT population, then tabulated and reported for each treatment arm and overall. Fisher's exact test will be used to assess differences which may be present between groups

Additionally, an overall summary of AEs will be provided including the number of events and percent of participants with any AEs, SAEs, and UADEs. For each type of event, the number of events and number and percent of participants with the event will be provided. Separate summaries of all adverse events will be summarized by seriousness and by relationship to device and procedure.

Only events occurring at or after the index procedure will be counted for the purpose of safety analysis. Events occurring prior to the index procedure will be considered as medical history.

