All mean and median values will be formatted to one more decimal place than the measured value. Standard deviation values will be formatted to two more decimal places than the measured value. Minimum and maximum values will be presented with the same number of decimal places as the measured value.

The number and percentage of responses will be presented in the form XX (XX.X%).

Version 1.0 Confidential Page 19 of 42

- All summary tables will include the analysis population sample size (i.e., number of patients).
- Relative Study Day 1 is defined as the day the patient underwent the DMR study procedure. All study days are determined relative to the day the patient underwent the DMR study procedure.
- Baseline values will be defined as those values recorded immediately prior to the DMR study procedure.
- Change from baseline for ratio data will be calculated as follows:

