### **Primary Endpoint**

The primary endpoint of the study is predicated on safety; the distribution of this endpoint is binary. The primary population for analysis of this endpoint will be the ITT population.

Proportion of patients experiencing one or more device- or procedure-related serious adverse events at 12 weeks post-procedure.

All device-related or procedure-related serious adverse events from the start of the study procedure through relative study day 84 will be used in the tabulation.

The secondary endpoints are listed below:

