### 10.1.2. Handling of Missing or Partial Adverse Event Dates

Handling of Missing AE Start-dates (missing AE stop-dates are not filled)

Rules for assuming a full date for AEs with incomplete or missing start-dates are addressed below. In the unusual case that the month portion of an AE start-date is missing but the day portion is not missing, the day portion of the AE will be assumed to be missing. Likewise in the case where the year portion of an AE start-date is missing but the month and/or day portion is not missing, the month and/or day portion of the AE will be assumed to be missing. All missing portion(s) of the AE start-dates will be handled using the same rules.

- In the event that the day portion (and only the day portion) of the AE onset date is missing:
  - o If the AE started in the same month and year as the study procedure, the AE onset date will be assumed to be the date of the study procedure (*i.e.*, Study Day 1);
  - Otherwise, the AE onset date will be assumed to be the 15th day of the given month and year, e.g., XX–DEC-2005  $\rightarrow$  15-DEC-2005 where XX represents an unknown value.
- In the event that the day and month portion (and only the day and month portion) of the AE onset date are missing:
  - o If the AE started in the same year as the study procedure, the AE onset date will be assumed the study procedure (*i.e.*, Study Day 1);
  - Otherwise, the AE onset date will be treated as June 15th of the given year, e.g., XX-XXX-2005 → 15-JUN-2005.

• In the event that the day, month, and year portion of the AE onset date are missing, the start-date of the AE will be assumed to be the study procedure (*i.e.*, Study Day 1).

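### SAP 7.3.4 and 10.1.2 impute incomplete AE onset dates differently with no stated precedence, and the 7.3.4 rule can date an early related SAE out of the primary safety endpoint

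*SAP*

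**What the plan says.** SAP 7.3.4 covers medical events in general and names AEs: "The completely or partially missing onset and resolution dates of medical events including AEs will be imputed in a conservative fashion as follows". For onset dates it gives three rules:

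- Day missing: "Use the first day of MM to impute the missing date part of the onset date".
- Month and day missing: "Use the first day of YYYY to impute the missing month and date parts of the onset date".
- Date wholly missing: "No imputation will be applied".

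SAP 10.1.2 covers the same AE start dates. If the known month and year match the procedure, "the AE onset date will be assumed to be the date of the study procedure"; otherwise the 15th of the month is used. If only the year is known, the procedure date is used when the year matches, and 15 June otherwise. A wholly missing date becomes the procedure date. The section then gives worked examples.

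The SAP does not say which section governs. SAP 7.3.1 exempts dates from its no-imputation rule, and SAP 7.3.3 concerns missing scores and observations, so neither settles the matter.

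The primary endpoint (SAP section 9) counts device- or procedure-related SAEs from the start of the procedure "through relative study day 84". At the lower end, Protocol 12.4.3 adds: "Events occurring prior to the index procedure will be considered as medical history". On numbering, SAP section 7 states: "Relative Study Day 1 is defined as the day the patient underwent the DMR study procedure". SAP 9.1 describes the same window as 84 days from the procedure.

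**The concern.** Whether an SAE counts in the primary endpoint depends on its onset date. Two programmers who follow this SAP on the same incomplete date can obtain different dates, and so different primary results. A choice between the rules made after the data are seen would be post hoc.

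The 7.3.4 rule takes no account of the procedure date. Moving an onset back to the start of its month or year is often called conservative because it lengthens the event. Here it can carry a post-procedure event to before the procedure, where the primary analysis does not count it. Events in the first days after the procedure are the ones most exposed, and they are central to a first-in-human device study.

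**Working it through.** **Inputs.** The two sets of rules (SAP 7.3.4 and 10.1.2), the worked-example patient in SAP 10.1.2 (procedure 04-FEB-2005, screening 18-JUL-2004), the primary window (SAP sections 7, 9 and 9.1), and N = 20, split 3 / 7 / 10 by treatment group (SAP section 3).

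**Step 1. Reproduce the SAP's examples.** Applying 10.1.2 gives all five of the SAP's stated results. Applying 7.3.4 gives none of them.

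| Recorded onset | 10.1.2 (as in the SAP) | 7.3.4 |
|---|---|---|
| XX-DEC-2004 | 15-DEC-2004 | 01-DEC-2004 |
| XX-FEB-2005 | 04-FEB-2005, Day 1 | 01-FEB-2005, 3 days before the procedure |
| XX-XXX-2004 | 18-JUL-2004 (reset to screening) | 01-JAN-2004 |
| XX-XXX-2005 | 04-FEB-2005, Day 1 | 01-JAN-2005, 34 days before the procedure |
| Wholly missing | 04-FEB-2005, Day 1 | no date |

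Rows 2 and 4 show the difficulty. The same SAE is inside the primary window under one section and before the procedure under the other.

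**Step 2. How often each rule dates an in-window event out.** Assumption: every procedure date in 2022–2023 (730 days) and every true onset 0 to 83 days later are equally likely, with only the day missing. That gives 730 × 84 = 61,320 combinations.

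- 7.3.4 dates out 10,746 / 61,320 = 17.5%, all of them to before the procedure.
- 10.1.2 dates out 2,520 / 61,320 = 4.1%, all of them past the upper limit. This ignores the 10.1.2 reset to an earlier AE stop date, which would recover some.
- No combination is lost under both, so the rules disagree on (10,746 + 2,520) / 61,320 = 21.6%.

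For true onsets 0–7, 0–14 and 0–28 days after the procedure, 7.3.4 dates 85%, 74% and 51% to before it. With only the year known, 7.3.4 dates out 88.4% of in-window onsets and 10.1.2 dates out 11.4%.

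**Step 3. The error also runs the other way.**

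- 7.3.4 pulls events in. With the procedure on 04-FEB-2005, a true onset of 30-APR is 85 days later and outside the window. With the day missing it becomes 01-APR, 56 days after, and counts. On the same uniform assumption, 7.3.4 wrongly counts about 49% of day-missing onsets that truly fall 84–113 days after the procedure.
- 10.1.2 pushes events out. With the procedure on 20-JAN-2022, a true onset of 05-APR is 75 days later. With the day missing it becomes 15-APR, 85 days after (relative day 86), and is lost. Here 7.3.4 gives 01-APR, 71 days after, and keeps it.

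**Step 4. Effect of one lost event (exact Clopper-Pearson 95% intervals).**

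- 1/20 = 5.0%, interval 0.1% to 24.9%.
- 0/20 = 0%, upper limit 1 − 0.025^(1/20) = 16.8%.
- By group, the estimate falls to 0 from 1/10 = 10%, 1/7 = 14.3% or 1/3 = 33.3%.

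**Step 5. The cut-off day.** With the procedure as Day 1, relative day 84 is 84 − 1 = 83 days after it: 28-APR-2005 for the example patient. Eighty-four days after is 29-APR-2005, relative day 85. The visit table in SAP 8.6 sets Week 1 at day 7 and Week 12 at day 84, which counts the procedure as day 0. The readings differ by one day.

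**The case against.** The case against giving this much weight is substantial.

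- **Likelihood.** Sites report SAEs to the sponsor within 24 or 36 hours (Protocol 9.3.2), onset date is a collected field, and discrepancies are queried (Protocol 14.2). An SAE without a full onset date should be rare. This stands.
- **Visibility.** Imputed values are flagged in the listings (SAP section 7), and a medical monitor adjudicates the device relationship of SAEs (Protocol section 10). A related SAE dated before the procedure would probably be noticed. This stands in part: neither document says that such a flag overrides the imputed date.
- **Likely practice.** 10.1.2 is specific to AEs and carries the worked examples, so a programmer would probably choose it. That is reasonable, but 7.3.4 names AEs explicitly and nothing gives 10.1.2 priority.
- **Medical history.** Protocol 12.4.3 speaks of events that occurred before the procedure. Applying it to an imputed date is an inference. Even without it, the SAP window opens at the procedure, so an earlier date is outside.

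A reader might infer that 7.3.4 can only remove events and so biases the safety proportion downward. The documents do not support that, because the rule also pulls late events in. With onsets spread evenly over 0–336 days and the day missing, it places 24.9% in the window, against a true share of 84/337 = 24.9%. A net downward effect needs related SAEs to cluster early. That is plausible, but it is an assumption about timing and does not follow from the rule. A reader might also infer that deleting the 7.3.4 rows is a complete cure. It is not, because 10.1.2 loses some late events.

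**Conclusion.** The contradiction is real and is shown by the SAP's own example patient, with no distributional assumption. For an event in the procedure month with the day missing, or in the procedure year with only the year known, 7.3.4 gives a date before the procedure unless the procedure fell on the first day of that month or year. Calling this conservative is wrong for early events.

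The percentages in Step 2 rest on uniform dates and describe only events whose onset is incomplete; they do not predict how many SAEs will be affected. The probability of any effect is low. If it happens, one patient moves the primary result by 5 percentage points overall and by more within a treatment group. The one-day difference in the cut-off is minor and matters only for an event exactly 84 days after the procedure. The point should be settled before database lock, but it does not put the design in doubt.

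**What to change.** 1. Remove the AE onset rows from SAP 7.3.4, or limit them to medical events other than AEs, so that 10.1.2 is the only rule for AE onset.
2. Add to 10.1.2 that no AE known to have started after the procedure is imputed to a date before it.
3. Add that a related SAE whose partial onset date is compatible with the primary window counts in the primary endpoint. This covers the upper end, where 10.1.2 alone can lose an event.
4. State the cut-off once, in SAP section 9 and in 9.1. Relative study day 85 matches 84 days after the procedure when the procedure is Day 1. Another day-count would serve if used throughout.

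The cost is SAP wording and the matching programming. No new data are needed. The safety proportion may become slightly less favourable, because a doubtful date would now count.
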